4.2.2 Secondary Endpoints

1. Frequency at which the patients undergo transplantation
2. Impact on quality of life
3. Post-transplant outcomes:
 - a. Overall Survival
 - b. Relapse

5.0 SUBJECT SELECTION

5.1 Inclusion Criteria

5.1.1 Disease Criteria

1. Diagnosis of *de novo* or secondary MDS, including chronic myelomonocytic leukemia, as defined by the 2008 World Health Organization Classification System.
2. Patients must have measurable disease requiring cytoreduction, defined as a bone marrow myeloblast count $\geq 5\%$ and $< 20\%$ on morphologic examination or by flow cytometry in cases in which adequate morphologic examination is not possible.

5.1.2 Age Criteria

1. Age ≥ 18 years

5.1.3 Organ Function, Performance Status and Other General Criteria

1. Patients must be considered to have an acceptable risk of early mortality with intensive chemotherapy as determined by the attending physician at the time of the initial visit. Since

the specific therapy within each arm will be determined after randomization, there is no threshold of organ dysfunction or performance status for inclusion.

2. Considered a potential transplant candidate. The attending/treating physician will determine transplant candidacy at the time of consent.
3. Capable of understanding the investigational nature, potential risks and benefits of the study, and able to provide valid informed consent.

5.2 Exclusion Criteria

1. A diagnosis of acute promyelocytic leukemia as defined by the 2008 World Health Organization Classification System.
2. Previous treatment for MDS or AML with intensive chemotherapy regimen (induction chemotherapy) or hypomethylating agent.
3. Have any other severe concurrent disease or have a history of serious organ dysfunction or disease involving the heart, kidney, liver, or other organ system that may place the patient at undue risk to undergo treatment.
4. Patients with a systemic fungal, bacterial, viral, or other infection not controlled (defined as exhibiting ongoing signs/symptoms related to the infection and without improvement, despite appropriate antibiotics or other treatment).
5. Females who are pregnant or breastfeeding.
6. Fertile men and women unwilling to use contraceptive techniques during and for 12 months following treatment.
7. Any uncontrolled or significant concurrent disease, illness, or psychiatric disorder that would compromise patient safety or compliance, interfere with consent, study participation, follow up, or interpretation of study results.
8. Clinical evidence suggestive of central nervous system (CNS) involvement with MDS unless a lumbar puncture confirms the absence of leukemic blasts in the cerebrospinal fluid (CSF).

6.0 SUBJECT REGISTRATION

[figure not shown]
[figure not shown]
Complete and submit the FHCRC Research Subject Registration Form (see Appendix A) with the signed informed consent to the FHCRC Research Coordinator, [contact].

After the eligible subjects have been registered, subjects will be randomized by the FHCRC Data Management Office (DMO), Monday through Friday between 8:30 and 4pm PST/PDT. FHCRC Research Coordinator will fax the randomization assignment back to the Study Coordinator at the outside site.

7.0 TREATMENT PLAN

Treatment Schema

This schema is a pictorial overview only; please see narrative sections of the protocol for specifics and allowable deviations from time frames shown.

Pre-treatment Determination of Eligibility and RandomizationTreatment Schema

5.3 7.1 Agent Administration

For patients enrolled on subsequent treatment protocols, the treatment regimen, including treatment agents, doses and method, timing and setting of administration (inpatient or outpatient) will be determined by the specific treatment protocol.

For patients who are not enrolled on other treatment protocols, the treatment regimen, including treatment agents, doses and method, timing and setting of administration (inpatient or outpatient) will be determined by the attending physician.

Although not mandatory, a suggested treatment for patients in Arm A is azacitidine intravenous or subcutaneous at 75 mg/m²/day for 7 days repeated every 28 (+/- 3) days [14]. For patients in Arm B, the suggested treatment is the "7+3" regimen, which combine a seven-day continuous intravenous infusion of cytarabine (100 or 200 mg/m² per day) with a short infusion or bolus of an anthracycline (idarubicin 10-12 mg/m² or daunorubicin 40-90 mg/m²) given on days one through three [15,16]. (See Appendix B)

7.2 Concomitant Medication and Supportive Care Guidelines

Supportive care measures (e.g. antibiotic prophylaxis and treatment, transfusion support) should be carried out according to institutional practice guidelines or the preference of the attending physician.

7.3 Screening

Bone marrow biopsy or aspirate for morphology must be collected within 60 days prior to Day 1 of treatment.

Within 30 days before Day 1 of treatment, perform these assessments

- Complete medical history and physical examination,
- CBC with differential
- Serum Chemistry
- Pregnancy test for women of childbearing potential
- EORTC-QLQ-C30 questionnaire

7.4 Duration of Therapy (Treatment Phase)

Duration of study therapy will depend on response and donor availability. Please see Appendix C for definitions of response criteria. For patients enrolled on concurrent treatment protocols, assessment of response as dictated by the treatment protocol will take precedence over the following treatment response evaluation and treatment duration guidelines.

The specific treatment agents and schedule will vary per patient within both study arms (please see section 7.1 for details). These agents and schedules will be determined by treatment protocols, institutional standards, or physician preference. Follow-up prior to each cycle of therapy will also be determined by treatment protocols, institutional standards, or physician preference.

Patients randomized to either arm must receive at least one cycle of therapy. If at any point after the administration of the first cycle of therapy a donor is available, the patient may proceed to HCT.

Patients may receive additional cycles of treatment to maintain response while waiting for donor availability. However, continued therapy should not be used to delay available HCT. If patients demonstrate disease progression at any point after the first cycle, they should discontinue the study treatment.

For patients who are receiving decitibine-based therapy under Arm A, it is recommended that a bone marrow biopsy or aspirate be obtained after 2 to 4 cycles to assess response. For patients who are receiving azacitidine-based therapy under Arm A, it is recommended that a bone marrow biopsy or

aspirate be obtained after 4 to 6 cycles to assess response. If at that point stable disease or better is achieved and a donor is available, the patient may proceed to HCT. If the desired degree of response or cytoreduction has not been met by 4 cycles of decitabine-based therapy, or 6 cycles of azacitidine-based therapy patients should be offered alternative treatments.

For patients randomized to Arm B, response to therapy will be determined by bone marrow biopsy or aspirate 28 (+/- 3) days after the start of therapy or at the time of count recovery. If a desired response is achieved, the patient may proceed to HCT. If a less-than desired response is achieved with the first cycle of intensive chemotherapy, it is recommended that the patient receive an additional cycle of intensive therapy (re-induction). If after re-induction a partial remission or better is achieved, the patient may proceed to HCT. However, if the patient has stable disease or disease progression, the patient should be offered alternative treatment or proceed directly to transplant if possible. .

If at any point a patient no longer desires to undergo HCT, or is no longer considered an HCT candidate, the patient will be withdrawn from the study. However, the patient may go on to receive the assigned treatment off study protocol.

The number and timing of clinic visits or scheduled inpatient admissions will be determined by either the primary treatment protocol or at the discretion of the attending physician.

Treatment phase evaluations are outlined in the study calendar (Appendix D). After initial treatment and before transplant, complete the EORTC-QLQ-C30 and EORTC-QLQ-HDC29 questionnaires.

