4.2 Endpoints

4.2.1 Primary Endpoint

18-month failure-free survival (failure defined as death or relapse)

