7.7 Criteria for Removal/Withdrawal

A patient must be discontinued from protocol-prescribed therapy under the following circumstances:

- Consent withdrawal at the patient's own request or at the request of their legally authorized representative;
- Any event that, in the judgment of the Investigator, poses an unacceptable safety risk to the patient;
- If, in the investigator's opinion, continuation in the study would be detrimental to the patient's well-being;

- Significant deviation from inclusion/exclusion criteria, in the opinion of the investigator;
- A positive pregnancy test at any time during the study;
- An intercurrent illness that, in the judgment of the investigator, would affect assessments of the clinical status to a significant degree and requires discontinuation of therapy, or
- Completion of the study

Once the attending physician has met and discussed the decision with the patient and/or family member, the Notice of Withdrawal from a Research Study form (see Appendix E) should be filled out. Complete this form only when the patient has withdrawn consent.

- It is the responsibility of the PI or his/her designee to complete the Notice of Withdrawal From a Research Study Form and fax it to the FHCRC Research Coordinator at [contact].

Study treatment is defined as "any activity involving a patient or donor described in a protocol that is not part of their routine medical care". Patients who withdraw from study treatment will be asked permission to continue to collect and record survival data up to the protocol-described end of the subject follow-up period.

Patients who are withdrawn from the protocol will not be replaced as this is intent to treat analysis.

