8.0 Adverse Event Reporting

Adverse events will not be reported as all AEs and SAEs that occur are considered to be related to treatment and would be considered "expected" side effects from standard of care treatment for either study arm. If patients are enrolled on an additional treatment protocol where they will receive an investigational drug, please refer to that protocol for a list of expected adverse events and event-capture procedures.

Patients who are not enrolled on this protocol who are not enrolled on an additional protocol, will receive standard therapies with FDA-approved medications. Please refer to the package insert of those medications for a listing of specific expected adverse events.

Death will be reported at the annual continuing review if it occurs within the participant's 18-month study participation period.

After the completion of treatment, patients will be tracked for progression and survival during the patient's 18-month study participation.

Outside sites will be required to report all deaths to the coordinating center that occur during subjects' 18-month participation period. Outside sites will communicate deaths to the coordinating center by email or fax. The coordinating center will maintain a death log for all protocol participants.

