13.0 STATISTICAL CONSIDERATIONS

Eligible patients will be randomized in a 1:1 fashion. The primary outcome will be analyzed on an intention-to-treat basis. It is not possible to enroll enough patients to this trial to show a statistically significant difference in overall survival between groups unless the assumed-true difference is unrealistically large. Instead, we have set a benchmark for “success” to be that the observed 18-month failure-free survival with hypomethylating agent-based treatment be at least as high as that in the intensive chemotherapy group. With 30 patients per arm, if the assumed-true survival probabilities are 50% and 30%, respectively, then the probability of observing an 18-month failure-free survival in the HMA group that is at least as high as that in the IC group is approximately 0.96. If the assumed-true probabilities are 45% and 30%, the probability of observing a success is approximately 0.91. On the other hand, if the 18-month failure-free survival in the HMA group and IC group is 50% and 60%, respectively, then the probability of observing a rate in the HMA group that is at least as high as that in the IC group is approximately 0.26.

The quality-of-life questionnaires will be scored. In addition to reporting the absolute scores, a distribution-based interpretation will be conducted using the standardized response mean to analyze changes in scores over time and differences between groups.

**Projected Target Accrual
ETHNIC AND GENDER DISTRIBUTION CHART**

TARGETED / PLANNED ENROLLMENT: Number of Subjects			
Ethnic Category	Sex / Gender		
	Females	Males	Total
Hispanic or Latino	1	1	2
Not Hispanic or Latino	24	34	58
Ethnic Category Total of All Subjects*	25	35	60
Racial Categories			
American Indian / Alaska Native	0	0	0
Asian	0	1	1
Native Hawaiian or Other Pacific Islander	0	0	0
Black or African American	1	1	2
White	24	33	57
Racial Categories: Total of All Subjects*	25	35	60

*The “Ethnic Category Total of All Subjects” must be equal to the “Racial Categories Total of All Subjects.”

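### Section 7.4 withdraws from the study patients who lose HCT candidacy or no longer want HCT, and no section says that relapse follow-up continues, although the intention-to-treat endpoint is death or relapse

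*Combined protocol and SAP*

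**What the plan says.** **Withdrawal.** Section 7.4 covers a patient who no longer wants transplantation, or who "is no longer considered an HCT candidate, the patient will be withdrawn from the study". It then allows the assigned treatment to go on outside the protocol.

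**Endpoint and analysis.** Section 4.2.1 gives the primary endpoint as "18-month failure-free survival (failure defined as death or relapse", and section 11.1 repeats the definition. Section 13.0 states: "The primary outcome will be analyzed on an intention-to-treat basis". Section 7.7 adds: "Patients who are withdrawn from the protocol will not be replaced as this is intent to treat analysis". Appendix C defines relapse only for patients who have reached CR or PR.

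**Data after withdrawal.** Section 7.7 is the only rule. For those who stop study treatment, its wording is that they "will be asked permission to continue to collect and record survival data up to the protocol-described end of the subject follow-up period". Study treatment is defined broadly, as "any activity involving a patient or donor described in a protocol that is not part of their routine medical care", so the clause plausibly reaches section 7.4 withdrawals. The removal list in 7.7 does not name loss of HCT candidacy, and of the withdrawal form it says: "Complete this form only when the patient has withdrawn consent".

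**Outcome recording in general.** Section 8.0 says that after treatment "patients will be tracked for progression and survival during the" 18 months of participation. Section 12.0 provides for progression, relapse and death to be recorded on every patient and points to Appendix I, which has been deleted. Appendix D schedules survival and relapse at 18 months after the first day of treatment. The Appendix H spreadsheet has an off-study date and a follow-up status column, but no relapse or death date.

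**The concern.** Loss of candidacy, or of the wish for transplantation, arises after randomization in an open-label trial. Sections 1.0 and 2.2 both say that pre-transplant treatment can affect candidacy. Section 2.4 cites a trial with comparable early treatment-related mortality and grade 3/4 toxicity in the two kinds of therapy. Withdrawal could therefore differ by arm, but the documents do not settle in which direction.

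Intention to treat needs death and relapse status to 18 months on every randomized patient. A site that follows 7.4 and 7.7 literally would have grounds to stop collecting relapse on a withdrawn patient and to keep only vital status, with permission. That conflicts with section 12.0, Appendix D and the intention-to-treat commitment. The patients at issue are withdrawn responders who later relapse and are alive at 18 months. Their death status is known, but their failure status may not be.

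The success rule in section 13.0 compares two observed proportions in 30 patients per arm, with no margin and no test. A few misclassified patients, spread unevenly, feed directly into the conclusion.

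**Working it through.** **1. The plan's own figures.** Section 13.0 declares success if observed failure-free survival (FFS) with HMA is at least as high as with IC, at 30 per arm. With X_H and X_I the failure-free counts,

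P(success) = Σₓ Pr(X_H = x) · Pr(X_I ≤ x), where X_H ~ Bin(30, p_H) and X_I ~ Bin(30, p_I).

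| True FFS, HMA/IC | Stated | Exact |
|---|---|---|
| 50% / 30% | 0.96 | 0.959 |
| 45% / 30% | 0.91 | 0.911 |
| 50% / 60% | 0.26 | 0.257 |

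All three reproduce. They presuppose complete outcome data on all 60 patients.

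**2. Model of the gap.** All 30 per arm are analysed and all deaths are known. Let w be the share of an arm withdrawn under 7.4, and u the share of those withdrawn patients who relapsed, are alive at 18 months, have no relapse recorded and are counted as non-failures. Then

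observed FFS = true FFS + w·u.

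The documents give neither w nor u. Both are assumptions: w = 10% in one arm and 20% or 30% in the other, in either direction, with u = 2-5% or 10-30%.

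**3. Worked case, 50%/30%.**
- IC 30% and HMA 10% withdrawn, u = 5%: HMA 0.50 + 0.10 × 0.05 = 0.505; IC 0.30 + 0.30 × 0.05 = 0.315; P(success) = 0.950.
- Same withdrawal, u = 30%: HMA 0.53, IC 0.39; P = 0.890.
- IC 10% and HMA 30% withdrawn, u = 5%: HMA 0.515, IC 0.305; P = 0.965.
- Same withdrawal, u = 30%: HMA 0.59, IC 0.33; P = 0.986.

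**4. Range over the unequal-withdrawal cases.**

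| True FFS, HMA/IC | Complete data | u = 2-5% | u = 10-30% |
|---|---|---|---|
| 50% / 30% | 0.959 | 0.950-0.965 | 0.89-0.99 |
| 45% / 30% | 0.911 | 0.896-0.922 | 0.80-0.96 |
| 50% / 60% | 0.257 | 0.231-0.282 | 0.125-0.43 |

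The expected number misclassified per arm is 30·w·u. At u = 2-5% that is 30 × 0.10 × 0.02 = 0.06 to 30 × 0.30 × 0.05 = 0.45 patients. At u = 10-30% it is 30 × 0.10 × 0.10 = 0.3 to 30 × 0.30 × 0.30 = 2.7.

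**5. Equal withdrawal.** With 10%, 20% or 30% withdrawn in both arms and u up to 30%, the largest change in the three cases is 0.008 (0.257 to 0.249 at 50%/60%).

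**6. Dependence on the handling rule.** Suppose instead that the whole outcome is missing in 10-30% of withdrawn patients, who have an assumed true FFS of 10%, and that withdrawal (IC/HMA) is 20/10, 30/10 or 10/30%. With r the missing share, observed FFS is p − 0.10·w·r if unknowns count as failures and p + 0.90·w·r if they count as non-failures.

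| True FFS, HMA/IC | As failures | As non-failures |
|---|---|---|
| 50% / 30% | 0.955-0.964 | 0.899-0.984 |
| 45% / 30% | 0.904-0.919 | 0.812-0.960 |

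Under these assumptions the choice of rule matters more than the missingness itself, and the plan states no rule.

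**The case against.** The strongest reply is that the protocol, read as a whole, means to ascertain everyone. Section 12.0 covers all patients. Appendix D ties the 18-month relapse check to the start of treatment and not to transplantation. Section 8.0 tracks progression and survival after treatment ends and has outside sites report deaths. Because 7.4 lets assigned treatment continue, withdrawal there might mean only leaving protocol treatment. This stands as evidence of intent, so it would be wrong to infer that the plan has no relapse follow-up. It does not remove the conflict: none of these sections says that it applies after a 7.4 withdrawal, and the one section on data after withdrawal names survival only.

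Other stronger readings also fail:
- *Withdrawn patients are dropped from the analysis.* Sections 7.7 and 13.0 point the other way, and nothing excludes them.
- *An unrecorded relapse is a non-failure.* No section says so. The main illustration is conditional on it.
- *The deleted Appendix I shows that relapse is not recorded.* A stale cross-reference to what is now Appendix H is just as plausible.
- *The bias favours a particular arm.* Sections 2.2 and 2.4 point different ways.

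The objection on size also has force. A patient contributes only if withdrawn, a responder, later relapsed, alive at 18 months and missed by routine recording. If 10% of withdrawn patients are truly failure-free, u = 30% needs at least 40% of them alive at 18 months. Nothing in the documents supports so high a figure. Finally, no protocol can obtain data from patients who refuse follow-up, so that loss is not in itself a defect. What is missing is a rule for handling it.

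**Conclusion.** The point holds as a conflict in the text that should be fixed. Sections 7.4 and 7.7, followed as written, can leave relapse unknown in randomized patients whose relapse status the endpoint and the intention-to-treat analysis require. Sections 8.0 and 12.0 and Appendix D show the opposite intent without resolving it.

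Bias needs three things together: relapses in withdrawn survivors going unrecorded, those patients being counted as non-failures, and withdrawal differing by arm. With low assumed non-capture (2-5% of withdrawn patients) the success probability moves by less than 0.03 in each of the plan's three cases. Only the larger assumed rates bring material shifts. The most consequential is at 50% HMA and 60% IC, where the chance of declaring success could rise from 0.26 to 0.43 although HMA is truly worse, or fall to 0.125 if the imbalance runs the other way. These ranges show sensitivity; they are not evidence that bias will occur. Confidence is medium, because the withdrawal rate, the non-capture rate and the direction are all unknown.

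**What to change.** - **7.4 and 7.7:** reconcile them with sections 12.0 and 13.0 and Appendix D, so that losing HCT candidacy or the wish for HCT does not end outcome follow-up. No treatment rule changes.
- **7.7:** extend the follow-up clause from survival to survival and relapse, collected to 18 months from existing clinical records or by contact, for all randomized patients unless consent to follow-up is withdrawn.
- **Appendix H and 12.0:** add relapse date and death date fields to the spreadsheet, and correct the reference to the deleted Appendix I.
- **13.0:** report the primary comparison with any remaining unknown outcomes counted first as failures and then as non-failures.

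The cost is amendment wording, two spreadsheet columns, chart review or a call for a few patients, and one additional run of the primary comparison. No new study procedure is needed.

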2.2 Clinical Data to Date

The strategy of using chemotherapy prior to transplantation in an attempt to reduce disease burden, therefore reducing the risk of relapse after HCT, has become commonplace. Nevertheless, in the absence of randomized prospective trials the role of pre-HCT cytoreduction remains undefined. Prior to 2004, the mainstay of cytoreduction was intensive chemotherapy regimens developed as induction therapy for AML though retrospective studies of these regimens before HCT have not pointed to a clear benefit [6-8]. Furthermore, intensive pre-HCT therapy may lead to a worsening in performance status impacting patients' candidacy for and capacity to tolerate the subsequent HCT [9].

More recently, hypomethylating agents (azacitidine and decitabine) have increasingly been used for pre-HCT cytoreduction rendered attractive by their ease of administration and a low toxicity profile in an attempt to better balance cytoreduction and treatment-related toxicity. In the absence of prospective data, several groups have published the results of retrospective analyses noting the feasibility of this approach [10-12]. We recently reported our experience in 68 patients who underwent HCT for MDS who received either induction chemotherapy or azacitidine prior to HCT [13]. The 1-year overall survival after transplant was 57% in the azacitidine group, and 36% in the group given induction chemotherapy. Although the risk of post-HCT relapse and non-relapse mortality was lower in the azacitidine group, none of the differences including overall survival were statistically significant suggesting that at a minimum azacitidine did not confer worse outcomes when compared to induction chemotherapy.

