11.3 Quality of Life Assessment

Quality of life will be assessed using the EORTC QLQ-C30 questionnaire and the QLQ-HDC29 module (Appendix G) at the following timepoints:

- EORTC QLQ-C30 questionnaire at the time of screening
- EORTC QLQ-C30 & QLQ-HDC29 at the completion of initial therapy prior to transplant
- EORTC QLQ-C30 & QLQ-HDC29 at 100 (\pm 14) days after stem cell infusion (Day +100)

The QLQ-C30 is a validated and widely used questionnaire to assess quality of life in cancer patients. The QLQ-HDC29 is treatment-specific quality of life questionnaire to QLQ-C30), that addresses treatment-specific side effects as well as emotional, social, and family issues for patients treated with high-dose regimens and HCT. The QLQ-HDC29 module is targeted to cover time during the treatment and up to 6 months post-treatment.

The QLQ-C30 is composed of both multi-item scales and single-item measures. These include five functional scales, three symptom scales, a global health status / quality-of-life scale, and six single items. Each of the multi-item scales includes a different set of items - no item occurs in more than one scale.

All of the scales and single-item measures range in score from 0 to 100. A high scale score represents a higher response level.

When the Quality of Life questionnaires are scored, the principle for scoring these scales is the same in all cases:

1. Estimate the average of the items that contribute to the scale; this is the raw score.
2. Use a linear transformation to standardize the raw score, so that scores range from 0 to 100; a higher score represents a higher ("better") level of functioning, or a higher ("worse") level of symptoms.

The QLQ-HDC29 module includes 29 items, consisting of 6 multi-item scales and 8 single-items. The scoring algorithms are similar to the scoring for the EORTC QLQ-C30. For the multi-item scales and single-item scales (except item 52) a high score is equivalent to worse or more symptoms/problems. For Spiritual item 52, a higher score indicates positive experience or less problems.

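### A patient withdrawn for leaving the transplant path before the one post-therapy quality-of-life form has no planned route to a score, and no rule handles the missing data

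*Combined protocol and SAP*

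**What the plan says.** Section 3.2 makes the effect of IC versus HMA on quality of life a secondary objective. The only reading between screening and HCT is described in Section 11.3 as "EORTC QLQ-C30 & QLQ-HDC29 at the completion of initial therapy prior to transplant". Section 7.4 gives the same window: "After initial treatment and before transplant, complete the EORTC-QLQ-C30 and EORTC-QLQ-HDC29 questionnaires". Appendix D repeats it, and the Appendix H data sheet has one column for it.

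Section 7.4 also contains the withdrawal rule, which applies at any time: if someone is "no longer considered an HCT candidate, the patient will be withdrawn from the study". A patient who has given up the wish for HCT falls under the same rule. The section then allows treatment to go on outside the study: "However, the patient may go on to receive the assigned treatment off study protocol". Section 7.7 says that patients who withdraw from study treatment "will be asked permission to continue to collect and record survival data". It does not mention questionnaires. It adds that withdrawn patients are not replaced because the analysis is by intention to treat. Section 13 applies intention to treat to the primary outcome.

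For quality of life, Section 13 plans to use the "standardized response mean to analyze changes in scores over time and differences between groups". It gives no method for missing scores.

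Section 1.0 expects treatment toxicity to affect candidacy for HCT. Section 2.2 is specific to one strategy: "intensive pre-HCT therapy may lead to a worsening in performance status impacting patients' candidacy".

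**The concern.** The standardized response mean (SRM) is the mean change divided by the standard deviation of the change, so a patient contributes only with both a screening and a post-therapy score. The plan removes patients from the study on an event that it expects toxicity to bring about, and it names no quality-of-life collection after that. Where the event comes before the form, the score is lost because the plan was followed, and plausibly for a reason tied to the outcome. The completer SRM would then describe patients who did well enough to be scored, when the objective concerns everyone randomised.

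This is separate from the Day 100 questionnaire, which by definition exists only after HCT. The pre-transplant reading is the one that could support a comparison of the arms as randomised.

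**Working it through.** **1. The plan's own figures.** The documents give no sample size, standard deviation, effect size or expected withdrawal rate for quality of life, so there is no stated figure to reproduce on this point. The three probabilities in Section 13 (0.96, 0.91, 0.26) concern the primary endpoint. They reproduce as P(X_HMA ≥ X_IC) for two independent binomials with n = 30 (0.959, 0.911, 0.257) and do not bear on this question.

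**2. What happens to each kind of patient under the text.**

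| Order of events | Post-therapy score under the plan |
|---|---|
| Stays on the HCT path, form completed | Yes |
| Form completed, then candidacy or wish for HCT lost | Yes; nothing discards it |
| Candidacy or wish for HCT lost before the form | No planned route |
| Dies before the form | None, under any withdrawal rule |

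Only the third row is created by Sections 7.4 and 7.7.

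**3. Bias within an arm (all inputs assumed).** Let w be the share of an arm withdrawn unscored, d the extra worsening in those patients on the 0-100 scale, and m the mean change in scored patients. The full-arm mean is (1 − w)m + w(m − d) = m − wd, so the completer mean looks wd points too good.

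- w = 10%, d = 10: 0.10 × 10 = 1 point
- w = 30%, d = 20: 0.30 × 20 = 6 points
- w = 40%, d = 30: 0.40 × 30 = 12 points

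If a fraction f of the withdrawn patients had already completed the form, w being the share withdrawn, the bias is wd − wfd / (1 − w(1 − f)). With w = 30% and d = 20 it is 6.0, 4.1, 2.5, 1.1 and 0 points at f = 0, 25%, 50%, 75% and 100%.

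On the SRM scale, take m = −5, a standard deviation of 20 and d = 20. The completer SRM is −5/20 = −0.25. The full-arm SRM is (m − wd) / √(20² + w(1 − w)d²): −0.34, −0.50 and −0.58 at w = 10%, 30% and 40%.

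**4. Bias between arms.** With the same d in both arms, the masked difference is (w_IC − w_HMA) × d.

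- Equal rates: 0 points
- 30% v 10%, d = 20: 4 points (21 and 27 of 30 scored)
- 40% v 10%, d = 30: 9 points (18 and 27 of 30 scored)

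Exchanging the rates reverses the sign.

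**5. Can the documents settle the direction?** The nearest proxy is the 18-month failure-free survival S assumed in Section 13, with a constant hazard (assumed): failed by week k = 1 − S^((7k/30.4375)/18). The times are taken from response assessment. For HMA they are 4 to 6 azacitidine cycles of 28 days, or weeks 16 to 24. For IC they are day 28, or week 8 if re-induction takes another 28 days (assumed).

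| Arm | S | Failed by the earlier time | Failed by the later time |
|---|---|---|---|
| HMA | 50% | 13.2% (week 16) | 19.1% (week 24) |
| IC | 30% | 6.0% (week 4) | 11.6% (week 8) |

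The differences are 13.2 − 6.0 = 7.2 and 19.1 − 11.6 = 7.5 points, with **more** loss on HMA because its form comes later. Section 2.2 suggests more loss of candidacy on IC. The two indications point in opposite directions. With a gap of 1 SD between unscored and scored patients, 7.2 points of difference would shift the contrast by 0.07 SD. The standard error, with n = 30(1 − w) per arm, is √(1/26.0 + 1/28.2) = 0.27 SD, so the shift is about a quarter of it. The proxy counts deaths and relapses, not withdrawals, so it is not an estimate of w.

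**The case against.** The strongest reply is that the gap is narrow and its effect unproven. The form is due when initial therapy ends, and Section 7.4 requires only one cycle before HCT becomes possible, so many patients may be scored before candidacy is lost. The endpoint is secondary, and Section 13 plans no test or power for it. These points stand, and they limit the severity.

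Three stronger readings are tempting, and the documents do not support them.

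- A reader might infer that no withdrawn patient can be scored. It depends on which comes first, the form or the withdrawal.
- A reader might infer that the patients left out are those harmed most by therapy. Sections 1.0 and 2.2 make a link with toxicity plausible, but candidacy can be lost for other reasons, such as progression, and the same rule removes patients who simply change their minds about HCT.
- A reader might infer that the comparison flatters IC. That needs more unscored patients on IC, or a larger gap among them. The documents give neither, and the timing of the forms points the other way.

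Early deaths do not count against the withdrawal rule, since they leave no score however it is worded. What survives every objection is that a patient withdrawn before the form has no planned route to a score, and the analysis has no rule for the gap.

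**Conclusion.** The concern holds in limited form. Read together, Sections 7.4, 7.7, 11.3 and 13 restrict the post-therapy quality-of-life analysis to patients scored before any withdrawal. The missingness is plausibly informative on the protocol's own reasoning, and would tend to understate quality-of-life loss within an arm. Under the assumed ranges the understatement runs from 1 to 12 points, shrinking to nothing if all withdrawn patients complete the form first. It rests on withdrawn patients having worsened more than the rest, which is likely but not documented. Bias between arms may be zero or of either sign, and its size is unknown. Only a secondary endpoint is affected. The change is worth making because it is cheap and bears directly on a stated objective.

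**What to change.** 1. **Sections 7.4 and 11.3.** State that loss of HCT candidacy, or of the wish for HCT, does not end quality-of-life follow-up. Consenting patients complete the post-therapy QLQ-C30 at completion or discontinuation of initial therapy, whether or not HCT is still planned. Tying the form to the end of therapy avoids measuring patients just as they learn that HCT is off.
2. **Section 7.7.** Extend the permission request from survival data to survival data plus this questionnaire. Reconcile withdrawal from the study in Section 7.4 with the continued follow-up and intention-to-treat wording in Section 7.7.
3. **Section 13.** Compare the post-therapy score by randomised arm among all patients who have one, including those off the HCT path. Report per arm the numbers scored, dead before assessment, and alive but not assessed. Label the completer SRM as descriptive.

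A sensitivity analysis for death before assessment is optional. It would need one named QLQ-C30 scale, since Section 11.3 lists five functional scales, three symptom scales, a global scale and six single items.

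The cost is protocol wording, one existing 30-item form by phone or mail for patients who leave the HCT path, and three counts per arm. No extra patients or procedures are needed, and treatment is unchanged. Some patients will decline, and the timing of the form will be somewhat less uniform.
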